While cannabis can vary widely in its ratio of its key components tetrahydrocannabinol (THC) and cannabidiol (CBD), both can dampen brain activity^{30,31} adversely influencing cognitive functioning^{32,33} and mood^{34,35}, and their respective neurobiological substrates^{36,37}. The problematic neuropsychiatric consequences are well known³⁷ and can be especially critical in the context of MS^{29,38-42}. The high prevalence of cannabis use in MS is a challenge for prospective study, with investigators instead demonstrating the therapeutic gains following its discontinuation, including restoration of aspects of brain activity⁴³, reduced depression⁴⁴, and improved cognitive functioning⁴³. The benefit to MS-related cognitive impairment is particularly urgent, given that it is among the most disabling disease features⁴⁵ and occurs in

CONFIDENTIAL

>75% of all patients at any point in their disease course^{46,47}. Initially characterized by slowed information processing⁴⁶, reduced cognitive functioning can be subtle but often disables otherwise neurologically intact patients, compromising the ability to meet both work and family responsibilities⁴⁸. Cannabis use causes further impairment^{37,49}, a finding that is consistent across other chronic brain disorders^{50,51}.

We propose to target the distress that perpetuates the addiction cycle.

Psychological distress⁵² is an emotional health status marked by negative affect (e.g., feeling anxious, agitated, tense, irritable). As described in Koob & Volkow's 3-stage model of addiction^{53,54}, negative emotional states^{52,55} are key drivers of the addiction cycle. Distress is a result of disordered cannabis use, and in turn, also drives its continued use (i.e. "to cope"). Distress resulting from the disordered use of cannabis is well documented^{56,57}, and patients with MS are likely to be at even greater vulnerability to the distress component of addiction⁵⁸⁻⁶². As the state of distress is often below the threshold of clinical depression or anxiety disorders, it remains an under-detected and undertreated aspect of the cannabis addiction cycle.

The dorsolateral prefrontal cortex (DLPFC) is a key neural circuit for negative affect⁶³⁻⁶⁶.

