3.2 Secondary Objectives

- To evaluate the presence of persisting benefits in distress through the 3-month follow-up.
- To evaluate the presence of persisting benefits in cannabis use through the 3-month follow-up.
- To evaluate the interactions between the dependent measures of the primary objectives. The interactions between the dependent measures will be evaluated to test the hypothesis that an RS-tDCS-related change in cannabis use metrics is linked to a change in distress.
- To evaluate the interactions between distress and cannabis use and the exploratory outcomes of cognitive and symptom measures.

4 Study Design and Endpoints

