4.1 Description of Study Design

This randomized, double-blinded, parallel-arm, sham-controlled study will recruit n=52 female MS patients (target is 42 patients plus 10% to account for screen fails and withdrawals) to be randomly assigned using a 2:1 randomization method to receive 20x20 min sessions of either active 2.0mA tDCS or sham tDCS, combined with simultaneous mindfulness meditation over a 4-6 week period. Groups will be matched on years of cannabis use (4 years or less vs. 5 or more years).

All participants will have a remote consent/research screening visit, baseline visit, 20 tDCS treatment visits, and 1-month, 2-month, and 3-month follow-ups. All visits will be completed remotely through Zoom or Webex. Study procedures will be the same for both groups, with the only difference being the tDCS stimulation setting of 2.0 mA active or sham.

This will be a single site study at NYU Langone Health and will take place over a 2 year period.

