5.1 Inclusion Criteria

In order to be eligible to participate in this study, an individual must meet all of the following criteria:

1. Ages 21-65 (inclusive)
2. Female
3. Seeking treatment to reduce or discontinue current cannabis use (smoke/vape/ingest)
4. Current Cannabis Use Disorder per DSM-V
5. K10 score 10-35, inclusive (mild to high moderate distress)
6. Definite MS diagnosis, relapsing remitting (RRMS) subtype
7. PDDS score 0-7 (mild to moderate neurological disability, established to be able to complete procedures)
8. All medications stable for \geq 1 month prior to enrollment and throughout the trial
9. Ability to understand the informed consent process and provide consent to participate in the study
10. Stable and continuous access to internet service, email (WiFi “hotspot” to be provided if needed)
11. Ability to use mobile devices
12. Fluent in English language (due to outcomes validated in English versions only)
13. WRAT-4 score \geq 85

Inclusion criteria may be confirmed through medical records, screening assessments and self-report.

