While the remote connection does allow for a participant to provide a sample that is not their own to test, we believe that this occurrence would be of very low likelihood in this study sample. The participants are enrolled based on disclosed cannabis use, they are not incentivized in any way to decrease their cannabis use, and there would be no other primary or secondary gain for invalidating this procedure. Alternatively, in the similarly unlikely event that participants have falsely reported cannabis use and test negative at baseline, they will be withdrawn.

- Participants will complete self-report questionnaires about their physical and mental health, and cannabis use through REDCap survey function (see assessments section 8.2 below).
- For exploratory research, participants will complete cognitive measures (BICAMS, Cogstate Brief Battery) and MS symptom questionnaires.
- Participants will have their first 20-minute tDCS session of either 2.0mA active or sham tDCS combined with mindfulness meditation. At each treatment session, participants will complete brief adverse event reports before and after each session. Once the study technician visually confirms correct headset placement and participants confirms adequate contact quality (moderate or good), the technician will provide the participant with a one-time use unlock code to enter into their tDCS device. The participant enters the code when ready to initiate the stimulation. During each stimulation session participants will listen to a guided mindfulness meditation audio track on the study provided laptop computer.
- Remotely-Supervised tDCS Sessions 2-20:
 - Over the next 4-6 weeks, participants will complete the remaining daily tDCS + mindfulness meditations as described above for session 1.
 - After sessions 5, 10, and 15 participants will complete self-report questionnaires using REDCap survey function.
 - tDCS session 20 & Treatment-end: After completing the final tDCS session participants will repeat the baseline self-report questionnaires and measures, and the single panel cannabis test. Participants will be asked to return the equipment via Fedex using a prepaid return label.
- Post treatment-end follow-ups

CONFIDENTIAL

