8.2.2 Cannabis Use Assessments

- Timeline Followback Method Assessment (TLFB)¹²⁵: self-report questionnaire to assess cannabis type and route of administration, frequency of use (number of days) and frequency of use during the day.
- Daily Sessions, Frequency, Age of Onset, and Quantity of Cannabis-Use Inventory (DFAQ-CU)¹²⁶: 41-item questionnaire to measure frequency, age of onset, and quantity of cannabis used
- Marijuana Craving Questionnaire-17 (MCQ-17)¹²⁷: 17-item questionnaire to assess marijuana craving.
- Cannabis Withdrawal Scale (CWS)¹²⁸: scale to quantify the intensity of withdrawal symptoms, as well as the amount of distress or impairment in functioning due to each symptom.
- Cannabis Single Panel Test⁵⁴: a single panel cannabinoid urine strip test will be used as secondary confirmation of the TLFB. Participant will be asked to collect a urine sample in a sterile urine sample cap right before the video visit. We will ask the participant to complete the test in real time through a live video connection with the study technician to verify and record the test strip reading. This strip test is made for the detection in human urine of cannabinoids and cannabis derivatives. The test is a qualitative assay (type "NO / YES"), and thus delivers a "negative" or "positive" result (cut-off: 50 ng/ml).
- The Cannabis Use Disorder Identification Test – Revised (CUDIT-R): 8-item screening instrument designed to identify potentially problematic or harmful recent cannabis use.

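### Hours since last cannabis use before the exploratory cognitive tests are neither set nor described as recorded, so the use-cognition association cannot separate test-day state from sustained change

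*Combined protocol and SAP*

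**What the plan says.** **Who is tested, and how.** Section 5.1 requires current use: "Seeking treatment to reduce or discontinue current cannabis use (smoke/vape/ingest". Section 8.1 says that participants who have "falsely reported cannabis use and test negative at baseline, they will be withdrawn", so those who continue are cannabinoid-positive at baseline. On setting, section 4.1 says: "All visits will be completed remotely through Zoom or Webex".

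**When.** For baseline, section 8.1 says: "For exploratory research, participants will complete cognitive measures (BICAMS, Cogstate Brief Battery) and MS symptom questionnaires". For treatment-end it says: "After completing the final tDCS session participants will repeat the baseline self-report questionnaires and measures". Section 8.3.6 repeats the cognitive measures at 3 months only.

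**What is recorded about use.** Section 8.2.2 describes three relevant instruments:
- The TLFB covers cannabis type, route, "frequency of use (number of days) and frequency of use during the day".
- The DFAQ-CU covers frequency, age of onset and quantity in 41 items, which are not listed.
- The urine strip gives a yes/no result at 50 ng/ml and serves to confirm the TLFB.

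**What is inferred.** Section 3.2 includes: "To evaluate the interactions between distress and cannabis use and the exploratory outcomes of cognitive and symptom measures". Section 4.2.3 names change in cannabis use in the corresponding exploratory endpoint. Section 10.4.6 analyses cognition much as the primary outcome, with an eye to disease burden. The supplementary covariates in section 10.2 contain no recency term.

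**The concern.** The background (section 2.1) says of THC and CBD that "both can dampen brain activity", with adverse effects on cognition and mood. If some of that effect is short-lived, a score depends partly on how recently the participant used before the test. A woman who moves from daily use to use on some days is less often tested soon after using. Her score can then rise although nothing durable has changed.

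The predictor (change in use) is thus tied to the test-day state that may move the outcome (change in score). Randomisation does not help, because change in use is not randomised. The 3-month repeat does not resolve it either, because the same information is missing there. At stake is how the use-cognition association is read: as recovery after cutting down, or as a less affected state on the day.

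**Working it through.** **Search of the plan.** The eligibility, procedures, assessment, schedule, prohibited-treatment and analysis sections contain no interval since last use before testing, no check for recent use at the visit and no hours-since-use item. The one restriction on cannabis during the study (section 8.5) concerns medical cannabis. A completed TLFB calendar might give last use to the nearest day. It would not separate use an hour before testing from use the evening before. The urine strip carries no timing.

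The plan gives no figure to reproduce here, so the size has to be illustrated.

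**Inputs from the plan.** 28 active and 14 sham (section 10.5); within-person correlation 0.8, borrowed from the intraclass correlation in the same section.

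**Assumed inputs, not in the plan.**
- Baseline share of days used: Beta(6, 1.5).
- Fall in share of days used: 40 points on active, 10 on sham, plus individual variation with SD 0.2; the share is kept between 0 and 1.
- Chance of use shortly before the test: k times the share of days used, with k = 0.5 to 0.8.
- Acute deficit d = 0.3 to 0.8 SD if tested after use; no lasting effect.

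**Expected size.** With no lasting effect, expected change in score = -d x k x (change in share of days used).
- Low end: d x k = 0.3 x 0.5 = 0.15, so a 40-point fall gives 0.15 x 0.40 = 0.06 SD.
- High end: d x k = 0.8 x 0.8 = 0.64, so a 40-point fall gives 0.64 x 0.40 = 0.26 SD.

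**How often the association test rejects.** Simulated two-sided 5% test of change in score against change in use, n = 42, 6000 trials per setting:

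| Acute deficit | k = 0.5 | k = 0.8 |
|---|---|---|
| 0 | 5% | 5% |
| 0.3 SD | 6% | 8% |
| 0.5 SD | 8% | 13% |
| 0.8 SD | 12% | 21% |

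Other runs of the same model put the top value between 19% and 22%, so the range is about 6-22%. With falls of 20 and 10 points the range is 6-15%, because individual variation in use still drives the association.

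**Share of the arm contrast that runs through test-day state.** The 30-point difference gives 0.15 x 0.30 = 0.045 SD to 0.64 x 0.30 = 0.19 SD. Bounding the share makes the simulated values 0.04 to 0.18 SD. Without an acute effect, the standard error is sqrt(2 x (1 - 0.8)) x sqrt(1/28 + 1/14) = 0.632 x 0.327 = 0.21 SD. The acute effect adds variance of its own, and at d = 0.8 the simulated standard error is about 0.27 SD. The component is therefore about 0.04/0.21 = 0.19 to 0.18/0.27 = 0.67 of a standard error.

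**The case against.** The strongest reply is that the cognitive tests are exploratory throughout (sections 4.2.3, 8.2.3 and 10.4.6), and that section 10.4.2 wants effect sizes for distress, negative affect and days of use, not for cognition. That stands, and it limits the point to interpretation of one exploratory association. It does not remove it, because section 3.2 lists that association among the secondary objectives.

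Four stronger readings are tempting, and the documents do not support them.

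- *Recency is definitely not collected.* The DFAQ-CU items and the TLFB form are not reproduced, so a last-use question cannot be excluded. What can be said is that none is described and no analysis uses one.
- *The arm difference in cognition would be spurious.* If active stimulation reduces use and fewer women are then affected when tested, that is a genuine consequence of assignment. The randomised contrast estimates a total effect, and the protocol does not claim to isolate a lasting part.
- *Craving and negative affect are distorted too, with recent use lowering scores.* Nothing in the documents says so, and section 2.1 points the other way for mood.
- *The primary results are at risk.* This point does not reach them. The K10, for example, asks about the past 4 weeks (section 8.2.1).

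It is also fair that section 2.1 does not distinguish acute from chronic effects, and that the size of the acute deficit is an assumption. Visits are by live video, so testing is not described as unsupervised, although no check for recent use is described.

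**Conclusion.** The gap is real but narrow. As described, the data cannot show whether an association between change in use and change in cognition reflects sustained change or test-day state. With no lasting effect, the nominal 5% test of that association rejects in about 6-22% of trials. This rests on the assumed acute deficit, chance of recent use and reductions in use. At the low end the distortion is negligible; at the high end the error rate is about four times nominal. The arm contrast stays valid as a total effect, and the primary endpoints are untouched by this point. It is a cheap improvement, not a flaw that threatens the trial.

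**What to change.** 1. First check whether the DFAQ-CU or the TLFB form in use already captures time of last use. If not, add one REDCap item, hours since last cannabis use, at the start of each cognitive battery (baseline, treatment-end, 3 months). Where a visit is split, ask it on the day the battery is taken.
2. In the exploratory use-cognition analysis, report the association with and without adjustment for change in recency. State before unblinding how long intervals are coded, since a participant who has stopped will have a very large value.
3. Label the adjusted analysis supportive. Recency arises after randomisation and is correlated with change in use, so with 42 people the adjusted estimate will be imprecise.
4. Interpret cognitive change as a total effect unless the association persists after that adjustment.

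There is no need for an identical interval since last use at every visit, which a participant who stops could not meet. Arm comparisons that exclude recent users are also not needed, because they would select on a variable that treatment affects.

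The cost is one extra item per battery and a small extra analysis. Hours since use on the test day cannot be reliably reconstructed later, so the item has to be in place when each battery is taken.

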5.7 Participant Withdrawal or Termination

5.7.1 Reasons for Withdrawal or Termination

Participants are free to withdraw from participation in the study at any time upon request. An investigator may terminate participation in the study if:

- Any clinical adverse event (AE), laboratory abnormality, or other medical condition or situation occurs such that continued participation in the study would not be in the best interest of the participant
- The participant meets an exclusion criterion (either newly developed or not previously recognized) that precludes further study participation.

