6.1.4 Dosing and Administration

The tDCS device will deliver each session 2.0 mA for 20 minutes over the DLPFC. Participants will receive 20 intervention sessions over the course of this study on weekdays (M-F).

Study technicians are always live with participants via Zoom or Webex when initiating and delivering the treatment and can address any issues that arise during treatment. Study technicians will direct headset placement remotely. The tDCS device can only operate if: **1)** the headset is correctly placed for adequate connection, and **2)** the study technician provides a session code that unlocks the device for a one-time only 20-minute period of use.

If the device loses adequate electrode contact for any reason, the device will automatically discontinue the session. The session can only be reestablished if another unlock code is provided by the study technician. Specific stop criteria are outlined for treatment administration. Should any stop criteria be met at any point in administration of treatment, the participant will not undergo any further treatments and will be asked to return the study equipment (See Fig 3). If the participant wishes to discontinue a session, they may press the "abort" key at any time, which ramps down and stops the stimulation current within 30 seconds.

CONFIDENTIAL

This material is the property of the NYU School of Medicine and Langone Medical Center. Do not disclose or use except as authorized in writing by the study sponsor
Interventional Template Version: 11 January 2019

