Participants will have 3 follow-ups at 1, 2 and 3 months post treatment-end to repeat the questionnaires. At the 3-month follow-up the participant's will also be given a single panel cannabis test and asked a brief blinding integrity questionnaire (i.e. which group they think they were in) and then unblinded.

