8.3.4 Remotely-Supervised tDCS sessions 2-19 (Visits 3-20)

- 20x20 minutes of active or sham tDCS with simultaneous mindfulness meditation (*20 minutes*)
- Self-report questionnaires will be administered through MyCap at sessions 5, 10, and 15 (*25 minutes*)
- AE reporting

8.3.5 tDCS Session 20 &Treatment-end Visit (Visit 21)

- Participants will complete tDCS session 20 (*20 minutes*)
- Repeat questionnaires and measures completed at baseline (*1 hour*)
- Perform the Cannabis 1 Panel Drug Test (*5 minutes*)
- Equipment return

CONFIDENTIAL

This material is the property of the NYU School of Medicine and Langone Medical Center. Do not disclose or use except as authorized in writing by the study sponsor
Interventional Template Version: 11 January 2019

[Last tDCS session and post-treatment questionnaires may be divided into two sessions +/- 3 days apart pending participant preference]

8.3.6 1, 2, and 3-month follow-up (months 2, 3, and 4, +/- 7 days) (Visits 22-24)

- Repeat questionnaires (30 minutes)
- Repeat cognitive measures and Cannabis 1 Panel Drug Test (only at 3-month follow-up) (35 minutes)
- Unblind after completing 3-month follow-up and brief blinding integrity questionnaire

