10.3 Analysis Datasets

Intent-to-Treat Analyses: All analyses will be performed on two samples: 1) the intent-to-treat sample consisting of all randomized subjects (n=52) and 2) the Per Protocol sample (individuals that completed all 20 sessions).

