13.5 Participant and Data Confidentiality

Information about study subjects will be kept confidential and managed according to the requirements of the Health Insurance Portability and Accountability Act of 1996 (HIPAA). Those regulations require a signed subject authorization informing the subject of the following:

CONFIDENTIAL

This material is the property of the NYU School of Medicine and Langone Medical Center. Do not disclose or use except as authorized in writing by the study sponsor
Interventional Template Version: 11 January 2019

- What protected health information (PHI) will be collected from subjects in this study
- Who will have access to that information and why
- Who will use or disclose that information
- The rights of a research subject to revoke their authorization for use of their PHI.

In the event that a subject revokes authorization to collect or use PHI, the investigator, by regulation, retains the ability to use all information collected prior to the revocation of subject authorization. For subjects that have revoked authorization to collect or use PHI, attempts should be made to obtain permission to collect at least vital status (i.e. that the subject is alive) at the end of their scheduled study period.

Participant confidentiality is strictly held in trust by the participating investigators, their staff, and the sponsor(s) and their agents. Therefore, the study protocol, documentation, data, and all other information generated will be held in strict confidence. No information concerning the study or the data will be released to any unauthorized third party without prior written approval of the sponsor.

The study monitor, other authorized representatives of the sponsor, representatives of the IRB or pharmaceutical company supplying study product may inspect all documents and records required to be maintained by the investigator, including but not limited to, medical records (office, clinic, or hospital) and pharmacy records for the participants in this study. The clinical study site will permit access to such records.

The study participant's contact information will be securely stored at each clinical site for internal use during the study. At the end of the study, all records will continue to be kept in a secure location for as long a period as dictated by local IRB and Institutional regulations.

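### Outcome assessments are triggered by session count, and the protocol schedules no efficacy assessment for a participant who stops tDCS early

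*Combined protocol and SAP*

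**What the plan says.** - **On-treatment assessments.** Section 8.1: "After sessions 5, 10, and 15 participants will complete self-report questionnaires using REDCap survey function". Sections 5.5 and 8.3.4 use the same session numbers. None of them gives a calendar date.
- **Treatment-end.** Section 8.1, under its session 20 bullet: "After completing the final tDCS session participants will repeat the baseline self-report questionnaires and measures, and the single panel cannabis test". Section 8.3.5 is headed "tDCS Session 20 &Treatment-end Visit (Visit 21"). Both primary endpoints in 4.2.1 are changes from baseline to this point.
- **Follow-up.** Section 8.1: "Participants will have 3 follow-ups at 1, 2 and 3 months post treatment-end to repeat the questionnaires".
- **Stopping.** When a stop criterion is met, 6.1.4 says that "the participant will not undergo any further treatments and will be asked to return the study equipment", and it points to Fig. 3. Section 5.7.1 opens with "An investigator may terminate participation in the study if" and lists two conditions. Section 5.7.2 says that a participant may withdraw. None of these sections mentions an outcome assessment at or after stopping.
- **Analysis.** Section 10.3 defines "the intent-to-treat sample consisting of all randomized subjects (n=52") and sets it beside a per-protocol sample of those with all 20 sessions. Section 10.4.2 fits a linear mixed model at Visits 1, 5, 10, 15 and 20. Section 10.4.4 brings compliance into the model for change in distress to end of treatment.

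**The concern.** An analysis of everyone randomised needs a planned attempt to measure everyone randomised. Here the event that makes an assessment fall due is receipt of a treatment session, so stopping treatment also stops measurement. People who stop because of discomfort, an adverse event or worsening may well differ in outcome from those who continue, and the schedule gives no way to find out.

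The stake is the effect estimate. Section 10.4.2 says that the pilot exists to supply effect sizes for a later grant application, so an inflated estimate would carry into the next trial. With 14 sham participants planned, each lost endpoint also counts, and an outcome that was not collected cannot be recovered later.

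**Working it through.** **1. Trace one early stopper.** Take a participant whose last session is number 7 of 20.

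| Assessment | What triggers it | Does it fall due? |
|---|---|---|
| Session 5 questionnaires | session 5 | yes |
| Session 10 and 15 questionnaires | sessions 10 and 15 | no |
| Treatment-end (primary) | session 20, Visit 21 (8.3.5) | no |
| 1-, 2- and 3-month follow-ups | time since treatment-end | no date to count from |

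**2. Try the other reading.** The reference in 8.1 to the final session could mean the last session received. The table of contents supports this: it lists a treatment-end visit within a week of the last session, as Visit 22. If sessions are evenly spread over 4 to 6 weeks, this participant would be assessed at 7/20 × 4 = 1.4 weeks to 7/20 × 6 = 2.1 weeks. K10 asks about the past 4 weeks (8.2.1), so between (4 − 2.1)/4 = 48% and (4 − 1.4)/4 = 65% of her recall period would lie before session 1. That value is not comparable with one taken at session 20. Neither reading gives a usable rule, and the two passages disagree.

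**3. Ask whether the analysis plan repairs it.**
- Section 10.5 takes change from V1 as the dependent variable, with four values per measure. A participant who stops at session 7 supplies one of the four. One who stops before session 5 supplies none.
- The mixed model uses the available values under missing-at-random. In effect it completes her course from participants in the same arm who continued. That estimates what would have happened had she continued.
- Section 10.4.2.1 argues that randomisation makes bias from missing data unlikely, but stopping happens after randomisation. Its 10% trigger for imputation is worded for independent variables, not outcomes.
- The compliance analysis in 10.4.4 needs end-of-treatment values from people with fewer than 20 sessions. The visit rules do not provide them.

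**4. Size.** The plan's own figure comes first: design effect 1 + (5 − 1) × 0.8 = 4.2, and 50 × 4.2/5 = 42, split 28 and 14. It reproduces.

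Number affected, taking the 52 in section 10.3:
- 3% stopping (from the over 97% completion in 2.2.2): 52 × 0.03 = 1.56, about 2.
- 10% (the drop-out rate in 10.5): 52 × 0.10 = 5.2, about 5.

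Assume that the same share p stops in both arms and that stoppers keep no benefit. The all-randomised effect is then (1 − p) times the completers' effect, so a completers-only contrast overstates it by 1/(1 − p):
- p = 0.03: 1/0.97 = 1.03.
- p = 0.10: 1/0.90 = 1.11.

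**5. What measuring stoppers would do to power.** The documents give no numerical effect size. A simple two-group comparison of 28 and 14 at one-sided 0.05 and 80% power implies d = (1.645 + 0.842) × √(1/28 + 1/14) = 0.814. With 52 participants split 2:1:

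| Stopping | Effect, all measured | Power, all measured | Power, completers only |
|---|---|---|---|
| 3% | 0.814 × 0.97 = 0.789 | 85% | 86% |
| 10% | 0.814 × 0.90 = 0.733 | 80% | 84% |

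**The case against.** **The plan is silent; it does not forbid.** A reader might infer that early stoppers are barred from the primary endpoint, or that they fall out of the intent-to-treat analysis. The documents do not say so. Section 6.1.4 ends treatment, not participation. Returning equipment is not a sign of leaving, because completers also return it and then have three remote follow-ups. The Schedule of Events has a treatment-end column separate from the session columns. Sections 10.3, 10.4.2.1 (a supportive analysis of those with at least one session) and 10.4.4 all presuppose outcome data from partial completers. Fig. 3, to which 6.1.4 refers, is missing from the text available here. All of this stands. What it shows is that the analysis expects data for which no section schedules a visit.

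**Data after leaving.** A reader might infer that only vital status is pursued, because 13.5 says that "attempts should be made to obtain permission to collect at least vital status". That sentence concerns revoked authorisation. Section 9.3 records adverse events for 7 days, and serious ones for 30 days, after the last day of participation, and follows unresolved events. The gap is confined to efficacy outcomes.

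**Size.** A reader might take 42 evaluable of 52 as a stopping rate of 10/52 = 19.2%, and an overstatement of 52/42 = 1.24. Section 5.6 counts enrolment from signed consent, and 4.1 says that the allowance covers screen failures, so 19% is only an upper bound. A reader might also infer bias in favour of active, since only that arm receives sustained current. The documents give no stopping rates by arm, 2.4.1 reports nobody abandoning a study through discomfort, and 8.1 places a tolerability test before session 1. Differential stopping is possible but unsupported. In the other direction, the over 97% figure comes from other populations; 2.3 notes that tDCS has not been studied in cannabis use disorder.

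**Choice of target.** An effect under continued treatment is a legitimate aim for a pilot. The plan would then have to say so, whereas 10.3 names all randomised participants.

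**Conclusion.** The point holds as a gap in the plan. The body text ties efficacy assessments to session numbers, does not separate stopping tDCS from leaving the study, and provides no efficacy visit for someone who stops. The passages on the final session, the last session and session 20 must be reconciled.

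The likely scale is small: about 2 to 5 of 52 participants, and an overstatement of about 3% to 11%. Those percentages rest on three assumptions: equal stopping in both arms, no retained benefit, and a completers-only contrast. The planned mixed model keeps the earlier scores of those who reached session 5, so its error is smaller or uncertain. This is a should-fix item: a cheap improvement, not a defect that invalidates the trial.

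**What to change.** - In 5.7 and 8.3, distinguish stopping tDCS from withdrawing consent to data collection.
- For anyone who stops tDCS without withdrawing that consent, collect the remaining questionnaires on the calendar dates on which they would have fallen. Hold the treatment-end assessment at one fixed time from session 1 within the planned 4 to 6 weeks, and date the three follow-ups from it.
- Use TLFB, which is retrospective, to cover days since the last contact.
- In 10.3 and 10.4.2, state that these values enter the intent-to-treat model. In 10.4.2.1, word the missing-data trigger for outcomes.
- Make 8.1, 8.3.5 and the table of contents agree on what defines treatment-end and on its visit number.
- In 15.3, state that the $100 treatment-end and $100 final payments apply whether or not all sessions were completed.

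The cost is protocol and SAP wording plus a few extra remote contacts. Visits are already remote, questionnaires run in any browser, and the payments already exist. No stop criterion, dose or treatment rule changes. The downside is that some outcomes will be off treatment, so the estimate may be slightly smaller. In the illustration above, at 10% stopping, power is 80% with everyone measured against 84% in completers only.
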